**Same shell as Table 14.3.5.1.1**

**Programming Note:** Visits include Screening, Baseline, Day 1, Day 7 Pre-Dose, Day 7 Post-Dose, Day 14 Pre-Dose, Day 14 Post-Dose, and Day 21; parameters include PR interval (msec), RR interval (msec), mean heart rate (beats/min) QRS interval (msec), QT interval (msec), and QTcF interval (msec); SOURCE: Listing 16.2.8.4.2

Table 14.3.6.2.2  
Summary of 12-Lead Electrocardiogram Interpretation by Study Visit  
Safety Population

Study Visit Category	Cohort-1 (N=XX) n (%)	Cohort-2 (N=XX) n (%)	Overall (N=XX) n (%)
Screening			
Normal	XX (XX.X%)	XX (XX.X%)	XX (XX.X%)
Abnormal, Not Clinically Significant	XX (XX.X%)	XX (XX.X%)	XX (XX.X%)
Abnormal, Clinically Significant	XX (XX.X%)	XX (XX.X%)	XX (XX.X%)
Baseline [1]			
Normal	XX (XX.X%)	XX (XX.X%)	XX (XX.X%)
Abnormal, Not Clinically Significant	XX (XX.X%)	XX (XX.X%)	XX (XX.X%)
Abnormal, Clinically Significant	XX (XX.X%)	XX (XX.X%)	XX (XX.X%)
Day 1			
Normal	XX (XX.X%)	XX (XX.X%)	XX (XX.X%)
Abnormal, Not Clinically Significant	XX (XX.X%)	XX (XX.X%)	XX (XX.X%)
Abnormal, Clinically Significant	XX (XX.X%)	XX (XX.X%)	XX (XX.X%)

Note: Percentages are n/Number of subjects in the Safety Population and respective Protocol Amendment\*100.

[1] The baseline value for each variable is the last observation recorded prior to the first dose of treatment.

SOURCE: Listing 16.2.8.4.1

**Programming note:** Continue for Day 7 Pre-Dose, Day 7 Post-Dose, Day 14 Pre-Dose, Day 14 Post-Dose, and Day 21.

Table 14.3.6.2.3  
Summary of QTcF Values by Study Visit  
Safety Population

Study Visit Category	Cohort-1 (N=XX) n (%)	Cohort-2 (N=XX) n (%)	Overall (N=XX) n (%)
Screening			
QTcF Value			
> 450 msec to ≤ 480 msec [1]	XX (XX.X%)	XX (XX.X%)	XX (XX.X%)
> 480 msec	XX (XX.X%)	XX (XX.X%)	XX (XX.X%)
> 500 msec	XX (XX.X%)	XX (XX.X%)	XX (XX.X%)
Baseline [3]			
QTcF Value			
> 450 msec to ≤ 480 msec [1]	XX (XX.X%)	XX (XX.X%)	XX (XX.X%)
> 480 msec	XX (XX.X%)	XX (XX.X%)	XX (XX.X%)
> 500 msec	XX (XX.X%)	XX (XX.X%)	XX (XX.X%)
Day 1			
QTcF Value			
> 450 msec to ≤ 480 msec [1]	XX (XX.X%)	XX (XX.X%)	XX (XX.X%)
> 480 msec	XX (XX.X%)	XX (XX.X%)	XX (XX.X%)
> 500 msec	XX (XX.X%)	XX (XX.X%)	XX (XX.X%)
QTcF Increase from Baseline [3]			
> 30 msec to ≤60 msec	XX (XX.X%)	XX (XX.X%)	XX (XX.X%)
> 60 msec	XX (XX.X%)	XX (XX.X%)	XX (XX.X%)

Note: Percentages are n/Number of subjects in the Safety Population and respective Protocol Amendment\*100.

[1] Percentages are based on the number of male subjects in the Safety Population.

[2] Percentages are based on the number of female subjects in the Safety Population.

[3] The baseline value for each variable is the last observation recorded prior to the first dose of treatment

SOURCE: Listing 16.2.8.4.2

**Programming note:** Continue for Day 7 Pre-Dose, Day 7 Post-Dose, Day 14 Pre-Dose, Day 14 Post-Dose, and Day 21.

Table 14.3.6.4  
Summary of Columbia-Suicide Severity Rating Scale (C-SSRS)  
Safety Population

C-SSRS Section C-SSRS Item	Cohort-1 (N=XX)		Cohort-2 (N=XX)		Overall (N=XX)	
	Pre-treatment (N=XX)	Post-treatment (N=XX)	Pre-treatment (N=XX)	Post-treatment (N=XX)	Pre-treatment (N=XX)	Post-treatment (N=XX)
Suicidal Ideation	XX (XX.X%)	XX (XX.X%)	XX (XX.X%)	XX (XX.X%)	XX (XX.X%)	XX (XX.X%)
Wish to be Dead	XX (XX.X%)	XX (XX.X%)	XX (XX.X%)	XX (XX.X%)	XX (XX.X%)	XX (XX.X%)
Non-Specific Active Suicidal Thoughts	XX (XX.X%)	XX (XX.X%)	XX (XX.X%)	XX (XX.X%)	XX (XX.X%)	XX (XX.X%)
Active Suicidal Ideation with Any Methods	XX (XX.X%)	XX (XX.X%)	XX (XX.X%)	XX (XX.X%)	XX (XX.X%)	XX (XX.X%)
Active Suicidal Ideation with Some Intent	XX (XX.X%)	XX (XX.X%)	XX (XX.X%)	XX (XX.X%)	XX (XX.X%)	XX (XX.X%)
Active Suicidal Ideation with Specific Plan	XX (XX.X%)	XX (XX.X%)	XX (XX.X%)	XX (XX.X%)	XX (XX.X%)	XX (XX.X%)
Suicidal Behavior	XX (XX.X%)	XX (XX.X%)	XX (XX.X%)	XX (XX.X%)	XX (XX.X%)	XX (XX.X%)
Actual Attempt	XX (XX.X%)	XX (XX.X%)	XX (XX.X%)	XX (XX.X%)	XX (XX.X%)	XX (XX.X%)
Subject Engaged in Non-Suicidal Self-Injurious Behavior	XX (XX.X%)	XX (XX.X%)	XX (XX.X%)	XX (XX.X%)	XX (XX.X%)	XX (XX.X%)
Interrupted Attempt	XX (XX.X%)	XX (XX.X%)	XX (XX.X%)	XX (XX.X%)	XX (XX.X%)	XX (XX.X%)
Aborted Attempt	XX (XX.X%)	XX (XX.X%)	XX (XX.X%)	XX (XX.X%)	XX (XX.X%)	XX (XX.X%)
Preparatory Acts or Behavior	XX (XX.X%)	XX (XX.X%)	XX (XX.X%)	XX (XX.X%)	XX (XX.X%)	XX (XX.X%)
Suicidal Behavior	XX (XX.X%)	XX (XX.X%)	XX (XX.X%)	XX (XX.X%)	XX (XX.X%)	XX (XX.X%)

Note: Percentages are n/Number of subjects in the Safety Population and respective Protocol Amendment\*100. The C-SSRS scale consists of a Baseline evaluation that assesses the lifetime and more recent experience (past 12 months) of the subject with suicidal ideation and behavior, a baseline evaluation that focuses on suicidality since Screening that occurs before first dose of study drug (all of which is summarized under "pre-treatment"), and a post-baseline evaluation ("post-treatment") administered at either Day 21 visit or early termination visit for discontinued subjects, which focuses on suicidality since the last study visit. Subjects are counted once for each C-SSRS section and once for each C-SSRS item answered "Yes" in pre-treatment and post-treatment.

SOURCE: Listing 16.2.8.6

Commercially Confidential Information

Commercially Confidential Information

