#### 11.2.1 Analysis of Primary (Safety) Endpoint Data

- Vital sign parameters outside the normal range will be listed and flagged for review.
- Orthostatic vital signs parameters for blood pressure outside the ranges specified in [Section 7.10](#) below will be listed and flagged for review.
- Descriptive statistics of absolute and change from Baseline (pre-dose) SBP, DBP, pulse rate, respiratory rate, and oral temperature at each timepoint, will be tabulated. The mean change from Baseline data will also be plotted across time.
- Twelve-lead ECG parameters will be listed with any values outside the normal range flagged. Descriptive statistics of absolute and change from Baseline (pre-dose) heart rate, PR, QRS, QT, and QTcF intervals at each timepoint, will be tabulated. The mean change from Baseline data will also be plotted across time.
- In addition, frequencies of QTcF data will be calculated according to the following categories:

For absolute values

- QTcF >450 msec (males) and >470 msec (females)
- QTcF >480 msec
- QTcF >500 msec

For change from Baseline

- QTcF increase >30 msec
- QTcF increase >60 msec

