#### 6.1.6. Analysis Visit Windows

Visits will be analyzed as scheduled. Unscheduled and/or repeated measurements will only be included if a scheduled measurement is not available and the unscheduled/repeated measurement falls within the analysis visit windows as described in Table 2. The windows follow the Schedule of Events in Table 1. Unscheduled/repeated measurements will be listed. Study day is defined in Section 6.1.8.

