### 9.3. Vital Signs

Descriptive summaries of observed values and changes from baseline will be calculated for supine systolic blood pressure (SBP), standing SBP, supine diastolic blood pressure (DBP), standing DBP, supine heart rate (HR), standing HR, respiration rate, and oral temperature by study visit for the Safety Population overall and by cohort. Shifts from baseline for SBP, DBP, and HR values below, within, or above the normal range will be provided by study visit for the Safety Population overall and by cohort. Vital sign parameters outside the normal range will be flagged in the listings. The mean change from baseline in each parameter will also be plotted by study visit. Abnormal vital signs are as follows:

Commercially Confidential Information

- SBP >140 mmHg
- SBP <90 mmHg
- DBP >90 mmHg
- DBP <60 mmHg
- HR >100 bpm
- HR <60 bpm
- Respiration rate >20 breaths/min
- Respiration rate <12 breaths/min
- Oral temperature >99.1 °F/37.2 °C
- Oral temperature <97.8 °F/36.5 °C

Orthostatic vital signs (blood pressure and heart rate) will also be summarized by position and study visit and by cohort. During the Pre-dose visit, baseline orthostatic vital signs will include 3 separate measurements and the average of the 3 baseline orthostatic vital signs measurements will be used for comparison to all post-treatment measurements. The average HR, SBP, and DBP will be presented in the pre-dose baseline summaries and each of the individual measurements will be listed for that study visit.

Orthostatic hypotension will be defined as a reduction in systolic blood pressure of 20 mmHg or more and/or a reduction in diastolic blood pressure of 10 mmHg or more, for the standing measurement compared to the supine or semi-supine measurement. The frequency and percentage of subjects with orthostatic hypotension will also be presented by cohort. Any confirmed orthostatic hypotension or clinically significant measurements that are associated with clinical symptoms will be recorded as AEs. Orthostatic vital signs parameters outside the ranges specified above will be flagged in the listings.

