#### **9.4.      Electrocardiograms**

12-lead ECGs will be obtained at Screening, Pre-dose, Day 1, Day 7, Day 14, and Day 21.

Descriptive summaries will be presented for ECG measures of PR interval, RR interval, mean heart rate, QRS interval, QT interval, and QTcF interval. Corrected QTc intervals will be calculated using Fridericia's correction formula. These summaries will be presented by study visit for the Safety Population overall and by cohort. The mean change from baseline (pre-dose) for each parameter will be plotted by study visit. Values outside the normal range will be flagged in the listings.

The number and percentage of subjects with normal, abnormal but not clinically significant, and abnormal and clinically significant ECG results will be summarized for the Safety population by study visit.

Additionally, QTcF data will be summarized by the following categories by study visit:

- QTcF > 450 msec to  $\leq$  480 msec
- QTcF > 480 msec
- QTcF > 500 msec
- Change from baseline > 30 msec to  $\leq$  60 msec
- Change from baseline > 60 msec

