**Same shell as Table 14.3.5.1.1**

**Programming note:** Visits include Screening, Baseline, Day 1, Day 7 Pre-Dose, Day 7 Post-Dose, Day 14 Pre-Dose, Day 14 Post-Dose, and Day 21; parameters include Temperature (C), Respiration Rate (breaths per min), Systolic Blood Pressure (mmHg), Heart Rate (bpm), Diastolic Blood Pressure (mmHg), and Weight (kg); SOURCE: Listing 16.2.8.3.1, Listing 16.2.8.3.2.

Table 14.3.6.1.2  
Shift from Baseline in Vital Signs by Study Visit  
Safety Population

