**Same shell as Table 14.3.5.1.2**

**Programming note:** Visits include Screening, Baseline, Day 1, Day 7 Pre-Dose, Day 7 Post-Dose, Day 14 Pre-Dose, Day 14 Post-Dose, and Day 21; parameters include Temperature (C), Respiration Rate (breaths per min), Systolic Blood Pressure (mmHg), Heart Rate (bpm), Diastolic Blood Pressure (mmHg), and Weight (kg); Add the following footnote: "Abnormal vital signs are as follows. CCI SBP >140 mmHg, SBP <90 mmHg, DBP >90 mmHg, DBP <60 mmHg, HR >100 bpm, HR <60 bpm, Respiration rate >20 breaths/min, Respiration rate <12 breaths/min, Oral temperature >99.1 °F/37.2 °C, Oral temperature <97.8 °F/36.5 °C" Update footnote to SOURCE: Listing 16.2.8.3.1, Listing 16.2.8.3.2

Table 14.3.6.1.3  
Summary of Orthostatic Vital Signs by Study Visit  
Safety Population

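### ECG and vital-sign summaries are promised per timepoint in the protocol, but the SAP pools 7 post-dose times on Day 1 and 4 on each of Days 7 and 14 into single blocks, with no readable rule for filling them

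*SAP*

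**What the plan says.** Protocol 11.2.1 lists these summaries under the primary safety analysis. For ECG, absolute values and changes from baseline in "heart rate, PR, QRS, QT, and QTcF intervals at each timepoint, will be tabulated". For vital signs, the same applies to "SBP, DBP, pulse rate, respiratory rate, and oral temperature at each timepoint, will be tabulated". Mean changes are also to be plotted across time.

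Protocol 7.8 uses the term time points for 30 min, 60 min, 2 h and 4 h after dosing. Protocol 7.9 gives the same kind of schedule for vital signs, and footnote 8 of the Schedule of Assessments adds a pre-dose reading.

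SAP 9.4 says of the ECG measures: "These summaries will be presented by study visit for the Safety Population overall and by cohort". SAP 9.3 summarises vital signs by visit and adds: "The mean change from baseline in each parameter will also be plotted by study visit". The shell for ECG Table 14.3.6.2.1 specifies "Visits include Screening, Baseline, Day 1, Day 7 Pre-Dose, Day 7 Post-Dose, Day 14 Pre-Dose, Day 14 Post-Dose, and Day 21". Vital-sign Table 14.3.6.1.1 opens the same way ("Visits include Screening, Baseline, Day 1, Day 7 Pre-Dose, Day 7 Post-Dose") and continues with the same blocks.

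**The concern.** Several scheduled readings per subject fall into one table block, and the readable SAP does not say whether the block holds their mean, the last, the highest, or every record. Two programmers could each defend a different table. The SAP does give explicit averaging rules for repeated baseline sensor and orthostatic readings (6.1.1), but none for serial ECGs or routine vital signs.

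At stake is the shape of any response after dosing. A short-lived change in QTcF, blood pressure or heart rate is what serial post-dose readings can show, and a by-visit mean or plot can dilute or miss it. The error has no fixed direction, because a highest-value rule would instead produce increases with no drug effect.

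**Working it through.** **Scheduled times against table blocks** (Schedule of Assessments with footnote 8; blocks from the notes to Tables 14.3.6.1.1 and 14.3.6.2.1):

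| Visit | Scheduled times | Shell blocks |
|---|---|---|
| Screening | 1 | 1 |
| Baseline | 1 | 1 |
| Day 1 | 1 pre-dose + 3 after dose 1 + 4 after dose 2 = 8 | 1 |
| Day 7 | 1 pre-dose + 4 = 5 | 2 |
| Day 14 | 1 pre-dose + 4 = 5 | 2 |
| Day 21 | 1 | 1 |
| Total | 21 | 8 |

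The single Pre-Dose blocks on Days 7 and 14 lose nothing. The loss is 7 post-dose times in one block on Day 1, across two doses, and 4 in one block on each of Days 7 and 14.

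**Is there a selection rule?** The readable visit rule, SAP 6.1.6, says "Unscheduled and/or repeated measurements will only be included if a scheduled measurement is not available". It governs substitution for a missing scheduled reading and does not choose among several scheduled readings on one day.

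**Does the Day 1 block include the pre-dose reading?** SAP 6.1.1 ties baseline to the Pre-dose visit, which leaves the Day 1 pre-dose reading no block other than Day 1. The shell footnotes define baseline as the last observation before the first dose, which could be that same reading. Day 1 would then be post-dose only. The two definitions do not settle it.

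**Effect on a mean change (illustration).** The documents give no effect size, peak time or SD. Assume a 15 ms QTcF rise only at 2 h after each dose:
- Day 1, mean of 7 post-dose times: 15 × 2/7 = 4.3 ms
- Day 1, pre-dose included: 15 × 2/8 = 3.75 ms
- Days 7 and 14, mean of 4: 15 × 1/4 = 3.75 ms
- Last reading (4 h): 0 ms
- A nominal 2 h row: 15 ms

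If the rise were the same at all times, the mean of the post-dose times and the last reading would both show 15 ms.

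Precision of a 2 h row with 30 subjects: let s be the time-point SD and t the single-tracing SD, and assume the triplicate mean is used. Then v = s² + t²/3, and the 95% half-width is 2.045 × √(2v)/√30.
- s/t = 6/5: v = 44.3, half-width 3.5 ms
- s/t = 12/6: v = 156, half-width 6.6 ms

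**Effect on QTcF counts (illustration).** Expected subjects of 30 with a Day 1 increase above 30 ms. The SD of the change is √(2v) at one time and √(v + v/7) for the mean of seven. The highest-value rows come from numerical integration checked by simulation. Ranges run over assumed s/t pairs 6/5, 7/7, 8/6, 10/6 and 12/6:

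| Rule | No effect | +15 ms at 2 h only |
|---|---|---|
| Mean of times | 0.0–0.4 | 0.0–0.8 |
| Last time | 0.0–1.3 | 0.0–1.3 |
| Highest triplicate mean | 0.1–5.6 | 2.9–10.6 |
| Nominal 2 h row | 0.0–1.3 | 1.7–5.9 |

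These counts treat a subject's readings within a day, and the baseline, as independent. That assumption matters. For the 12/6 pair with no effect, the highest-value count of 5.6 falls to 1.6 if time-point readings correlate at 0.5 within a day and baseline is taken that day, and to about 0.09 at a correlation of 0.8. All 30 subjects are also placed on the current schedule, although Cohort-1 differed (SAP 3.4).

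**The case against.** **The word is used loosely.** Protocol 7.7 says timepoints for examinations done once per visit, and SAP 9.7 uses timepoint for biomarkers tabulated by visit. A by-visit reading of 11.2.1 therefore cannot be ruled out. That stands, but it does not close the gap: a by-visit table still has to say which of 7 or 4 readings it reports.

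**Safeguards exist.** The investigator reads the ECGs, clinically significant findings become AEs (Protocol 7.1), and out-of-range values are flagged in listings with individual times. This stands and limits the consequence. It does not supply the tabulated and plotted time course.

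**Redaction.** SAP 6.1.3 and part of section 10 cannot be read. A selection rule or a declared change may be there, so its absence cannot be asserted. The visible shells would still not be by timepoint.

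**Stronger readings that a reader might infer, and that the documents do not support:**
- That the Day 1 block certainly mixes pre- and post-dose values. The shell baseline footnote can remove the mixing.
- That the SAP breaks a protocol promise in the QTcF-category, vital-sign shift and ECG-interpretation tables. The timepoint wording covers values and changes only. QTcF frequencies are a separate item in 11.2.1 without it, and the other two tables are not requested there.
- That Listing 16.2.8.4.2 shows one value per triplicate. Each tracing has its own recorded time, so one row per tracing fits equally well.
- That the simulated counts measure the error in this trial. Their SDs, effect and independence are all assumed.

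**Conclusion.** The point holds in a limited form. SAP 9.3, 9.4 and Tables 14.3.6.1.1 and 14.3.6.2.1 report by visit what Protocol 11.2.1 says will be tabulated per timepoint, and no readable text says what a Day 1 or Post-Dose block contains. The block count follows directly from the schedule and the shells. The reduction from 15 ms to 4.3 ms or 0 ms depends on the assumed short-lived effect and on which rule is applied.

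The damage is confined to supporting descriptive safety tables and plots. The primary endpoint, the occurrence and severity of treatment-emergent AEs, is not altered by how these blocks are filled. It is worth fixing because the readings are scheduled anyway and the ambiguity is cheap to remove.

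**What to change.** 1. In SAP 9.3, 9.4 and Tables 14.3.6.1.1 and 14.3.6.2.1, tabulate and plot values and change from baseline by nominal time, with Day 1 pre-dose separate. Show Cohort-1 at the times its amendment scheduled, and fill the Overall column only for times common to both cohorts.
2. State how each ECG triplicate is reduced to one value (for example its mean), at baseline and at every later time. Make SAP 6.1.1 and the shell footnotes name the same baseline reading.
3. For the QTcF categories (SAP 9.4, Table 14.3.6.2.3), state the per-subject rule and show counts by nominal time. A count on each subject's highest post-dose value is an optional addition. It includes chance flags, so it belongs beside the nominal-time rows.
4. Declare any remaining departure from Protocol 11.2.1 in SAP section 10.

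The cost is SAP text and extra rows (up to 21 blocks instead of 8 on the current schedule), with no new assessments for subjects on that schedule. Cohort-1 rows need the Amendment 1 assessment times, which are not in these documents.

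Separately, Protocol 7.8 gives two ECG schedules for Days 7 and 14. One includes readings after the first daily dose, which Protocol 6.1.4 has taken at home. These passages must be reconciled with each other before the list of nominal times is fixed.

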#### **3.2. Sample Size and Power**

Up to 30 subjects will be enrolled. No formal statistical power analysis was conducted.

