## 4. Statistical Analysis and Reporting

### 4.1. Introduction

Data processing, tabulation of descriptive statistics, calculation of inferential statistics, and graphical representations will be performed primarily using SAS (release 9.4 or higher).

Commercially Confidential Information If the use of other software is warranted, the final statistical methodology report will detail what software was used for what purposes.

Continuous (quantitative) variable summaries will include the number of subjects (n) with non-missing values, mean, standard deviation (SD), median, minimum, and maximum.

Categorical (qualitative) variable summaries will include the frequency and percentage of subjects who are in the particular category for each possible value. In general, the denominator for the percentage calculation will be based upon the total number of subjects in the study population, unless otherwise specified. The denominator for by-visit displays will be the number of subjects in the relevant study population with non-missing data at each visit. If there is any missing value for a categorical analysis, a “Missing” category will be displayed as the last category in the table for the variable.

For weight, height, CCI one decimal place will be used for all summary statistics. For all other summaries, the minimum and maximum will be reported with the same degree of precision (i.e., the same number of decimal places) as the observed data. Measures of location (mean and median) and confidence interval boundaries will be reported to 1 degree of precision more than the observed data, up to 3 decimal places. Measures of spread (SD) will be reported to 2 degrees of precision more than the observed data, up to 3 decimal places.

Percentages will be presented to 1 decimal place, unless otherwise specified. Percentages equaling 0 or 100 will be displayed with no decimal places or percentage symbols.

Fractional numeric values will be presented with a zero to the left of the decimal point (for example, 0.12 – 0.30).

Unless otherwise indicated, all statistical tests will be conducted at the 0.05 significance level using 2-tailed tests, and *P* values will be reported. Corresponding 95% confidence intervals (CIs) will be presented for statistical tests, where applicable.

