## 5. Analysis Populations

The following analysis populations are planned for this study:

- **Safety Population:** The Safety population includes all subjects who took at least 1 dose of study drug, regardless of the Protocol Amendment under which subjects were enrolled. This population will be used to summarize all safety data.

- **Full Analysis Set (FAS):** The FAS consists of subjects in the Safety Population at least one TETRAS-PS assessment Total Score at Day 7, Day 14 or early termination visit. The FAS will be used to summarize all efficacy data.

Commercially Confidential Information

- **Per-Protocol Population:** The Per-Protocol Population includes all subjects in the FAS who did not have any major protocol deviation and follow the study protocol for TETRAS-PS assessment at Day 14 or ET visit.

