0	XX (XX.X%)	XX (XX.X%)	XX (XX.X%)	XX (XX.X%)	XX (XX.X%)	XX (XX.X%)	XX (XX.X%)	XX (XX.X%)
0.5	XX (XX.X%)	XX (XX.X%)	XX (XX.X%)	XX (XX.X%)	XX (XX.X%)	XX (XX.X%)	XX (XX.X%)	XX (XX.X%)
1	XX (XX.X%)	XX (XX.X%)	XX (XX.X%)	XX (XX.X%)	XX (XX.X%)	XX (XX.X%)	XX (XX.X%)	XX (XX.X%)
1.5	XX (XX.X%)	XX (XX.X%)	XX (XX.X%)	XX (XX.X%)	XX (XX.X%)	XX (XX.X%)	XX (XX.X%)	XX (XX.X%)
2	XX (XX.X%)	XX (XX.X%)	XX (XX.X%)	XX (XX.X%)	XX (XX.X%)	XX (XX.X%)	XX (XX.X%)	XX (XX.X%)
2.5	XX (XX.X%)	XX (XX.X%)	XX (XX.X%)	XX (XX.X%)	XX (XX.X%)	XX (XX.X%)	XX (XX.X%)	XX (XX.X%)
3	XX (XX.X%)	XX (XX.X%)	XX (XX.X%)	XX (XX.X%)	XX (XX.X%)	XX (XX.X%)	XX (XX.X%)	XX (XX.X%)
3.5	XX (XX.X%)	XX (XX.X%)	XX (XX.X%)	XX (XX.X%)	XX (XX.X%)	XX (XX.X%)	XX (XX.X%)	XX (XX.X%)
4	XX (XX.X%)	XX (XX.X%)	XX (XX.X%)	XX (XX.X%)	XX (XX.X%)	XX (XX.X%)	XX (XX.X%)	XX (XX.X%)
Face (including jaw) Tremor								
0	XX (XX.X%)	XX (XX.X%)	XX (XX.X%)	XX (XX.X%)	XX (XX.X%)	XX (XX.X%)	XX (XX.X%)	XX (XX.X%)
0.5	XX (XX.X%)	XX (XX.X%)	XX (XX.X%)	XX (XX.X%)	XX (XX.X%)	XX (XX.X%)	XX (XX.X%)	XX (XX.X%)
1	XX (XX.X%)	XX (XX.X%)	XX (XX.X%)	XX (XX.X%)	XX (XX.X%)	XX (XX.X%)	XX (XX.X%)	XX (XX.X%)
1.5	XX (XX.X%)	XX (XX.X%)	XX (XX.X%)	XX (XX.X%)	XX (XX.X%)	XX (XX.X%)	XX (XX.X%)	XX (XX.X%)
2	XX (XX.X%)	XX (XX.X%)	XX (XX.X%)	XX (XX.X%)	XX (XX.X%)	XX (XX.X%)	XX (XX.X%)	XX (XX.X%)
2.5	XX (XX.X%)	XX (XX.X%)	XX (XX.X%)	XX (XX.X%)	XX (XX.X%)	XX (XX.X%)	XX (XX.X%)	XX (XX.X%)
3	XX (XX.X%)	XX (XX.X%)	XX (XX.X%)	XX (XX.X%)	XX (XX.X%)	XX (XX.X%)	XX (XX.X%)	XX (XX.X%)
3.5	XX (XX.X%)	XX (XX.X%)	XX (XX.X%)	XX (XX.X%)	XX (XX.X%)	XX (XX.X%)	XX (XX.X%)	XX (XX.X%)
4	XX (XX.X%)	XX (XX.X%)	XX (XX.X%)	XX (XX.X%)	XX (XX.X%)	XX (XX.X%)	XX (XX.X%)	XX (XX.X%)

Abbreviations: TETRAS-PS = Tremor Research Group Essential Tremor Rating Assessment Scale (TETRAS)-performance subscale (PS).

Note: Percentages are n/Number of subjects in the respective population and cohort at each visit\*100. TETRAS-PS Total score is derived as the sum of all of the individual item scores, with the exception of item 5, only the maximum of the lower limb tremor scores will be counted. Each individual item question score ranges from 0 to 4, where higher scores indicate worse quality of life.

[1] The baseline value is the last observation recorded prior to the first dose of treatment.

SOURCE: Listing 16.2.6.1.1

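### The notes of the by-visit safety shells divide by the whole Safety Population, contradicting SAP Section 4.1 and understating category percentages whenever values are missing

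*SAP*

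**What the plan says.** SAP Section 4.1 gives a general rule and then a specific one. In general, "the denominator for the percentage calculation will be based upon the total number of subjects in the study population, unless otherwise specified". For visit tables: "The denominator for by-visit displays will be the number of subjects in the relevant study population with non-missing data at each visit". The same paragraph calls for a Missing category, beginning "If there is any missing value for a categorical analysis".

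The shells in SAP Section 14.2 say something else. The notes to Tables 14.3.5.1.2 (laboratory shifts), 14.3.5.3.3 (qualitative urinalysis), 14.3.6.1.5 (orthostatic shifts), 14.3.6.1.6 (orthostatic hypotension), 14.3.6.2.2 (ECG interpretation) and 14.3.6.2.3 (QTcF) all read "Percentages are n/Number of subjects in the Safety Population and respective Protocol Amendment". Tables that reuse these shells, such as the chemistry and vital sign shifts, inherit the note. Section 5 defines that population by dosing alone: "The Safety population includes all subjects who took at least 1 dose of study drug".

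The categorical efficacy shell, Table 14.2.1.1.3, uses a per-visit base: "Percentages are n/Number of subjects in the respective population and cohort at each visit". In the QTcF shell, the row above 450 up to 480 msec carries a further footnote: "Percentages are based on the number of male subjects in the Safety Population".

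**The concern.** A programmer cannot satisfy both Section 4.1 and the shell notes once any value is missing. Section 10 of the SAP, as far as it is visible, declares no departure from the Section 4.1 rule.

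Missing values at the later visits are foreseeable. One dose is enough to enter the Safety Population, and SAP Section 6.1.5 says withdrawn subjects were not replaced. Protocol Section 6.2 gives early terminators the Day 14 procedures but no in-clinic dose, so that visit cannot supply a Day 14 post-dose value. Protocol Sections 6.1.6 and 6.2 describe the Day 21 visit for subjects who complete treatment.

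Safety is the primary objective, there is no control arm, and the sample is small: "Up to 30 subjects will be enrolled. No formal statistical power analysis was conducted". The absolute percentages are therefore what a reader will take from these tables. The risk is greatest for QTcF and orthostatic hypotension. Their shells list only event rows, with no Missing row and no n per visit, so within the table an unmeasured subject looks the same as one measured and free of the event.

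**Working it through.** The documents state no percentage, dropout rate or missing rate for these tables, so there is no plan figure to reproduce. The check compares the two instructions.

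**Inputs.** N = subjects treated, taken as 30 from SAP Section 3.2. m = subjects with no value at a visit, which is not given and is assumed at 0, 3, 6 or 9 of 30 (0 to 30%). x = subjects in a category at that visit (illustrative).

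**Formulas.**
- Shell note: x / N
- Section 4.1: x / (N − m)
- Ratio of shell to Section 4.1: (N − m) / N = 1 − m/N

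The shell figure is therefore too low by the relative amount m/N.

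| m of 30 | x = 2, shell | x = 2, Section 4.1 | x = 3, shell | x = 3, Section 4.1 | Relative shortfall |
|---|---|---|---|---|---|
| 0 | 6.7% | 6.7% | 10.0% | 10.0% | 0% |
| 3 | 6.7% | 7.4% | 10.0% | 11.1% | 10% |
| 6 | 6.7% | 8.3% | 10.0% | 12.5% | 20% |
| 9 | 6.7% | 9.5% | 10.0% | 14.3% | 30% |

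**Every category shrinks.** Take ECG interpretation with 24 of 30 measured: 18 normal, 4 abnormal but not clinically significant, 2 abnormal and clinically significant. The shell gives 60.0%, 13.3% and 6.7%, which sum to 80%. Section 4.1 gives 18/24 = 75.0%, 4/24 = 16.7% and 2/24 = 8.3%, which sum to 100%.

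**Cohort columns.** With an assumed cohort of 15, 3 unmeasured and 1 event, the figures are 1/15 = 6.7% and 1/12 = 8.3%. The relative shortfall is 3/15 = 20%, the same as for 6 of 30.

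**The exception.** If the QTcF row above 450 up to 480 msec counts both sexes but divides by males only, it exceeds the Section 4.1 figure whenever the number of males is below the number measured. With 2 subjects in the band and 24 measured, Section 4.1 gives 2/24 = 8.3%. The male-only base gives 2/10 = 20.0%, 2/15 = 13.3% or 2/20 = 10.0% for 10, 15 or 20 males (assumed). If the numerator is also restricted to males, women in that band appear nowhere in the table.

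**The case against.** The strongest defence is that the notes only need tidying. Several parts of it have weight.

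- *The shells may count as specifying otherwise.* The qualifier in Section 4.1 belongs to the general rule. The by-visit sentence follows without one, and no visible text gives shell notes precedence.
- *Missing will be shown.* Sections 4.1, 13 and 14.1 all ask for a Missing category, and shells 14.3.5.1.2 and 14.3.6.1.5 already print one. That discloses the gap but leaves the base unchanged. Section 4.1 is itself loose here, since it asks for a Missing category beside a non-missing base.
- *The measured n can be found elsewhere.* Tables 14.3.6.2.1 and 14.3.6.1.3 print n per visit, so a reader can rework QTcF and orthostatic hypotension. ECG interpretation draws on a different listing from its companion table, and qualitative urinalysis has no companion.
- *Few values may be missing.* This is a 14-day study, and SAP Section 6.1.6 lets an in-window unscheduled value stand in for a missing scheduled one. This is fair: with complete data the conflict has no effect.
- *The per-visit figure is not unbiased either.* If subjects leave because of poor tolerability, x/(N − m) treats them as like those who stayed. This stands. Following Section 4.1 restores consistency but does not solve informative dropout.

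A reader might also infer that all these shells count unmeasured subjects as event-free, or that the error always flatters the drug. The documents support neither. The shift shells show Missing. In ECG interpretation and urinalysis an unmeasured subject falls in no row, and Normal percentages drop too. The male-only QTcF row can err upwards.

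**Conclusion.** The concern holds: the shell notes are wrong as written, with minor to moderate severity. They contradict Section 4.1 and differ from efficacy shell 14.2.1.1.3. Apart from the male-only QTcF row, each category percentage is too low by the relative amount m/N. For 3 events of 30, the table prints 10.0% where Section 4.1 gives 11.1% with 3 unmeasured or 12.5% with 6. The size rests wholly on the assumed missing rate.

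The practical concern is greatest for the QTcF and orthostatic hypotension tables. The primary endpoint is not touched: the TEAE tables are not by-visit displays, and the Safety Population is the appropriate base for them.

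Two further inferences should be resisted. The shortfall grows over visits only if missing values accumulate, which the documents do not establish. Nor does a small cohort worsen it at a given missing rate, because the shortfall depends on m/N alone.

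**What to change.** In shells 14.3.5.1.2, 14.3.5.3.3, 14.3.6.1.5, 14.3.6.1.6, 14.3.6.2.2 and 14.3.6.2.3, and in the tables that reuse them:

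1. Change the note so that the base is the members of the Safety Population in that cohort who have a value at the visit. For shifts and changes, require a value at both Baseline and the visit.
2. Print that n for each visit and cohort column.
3. Show Missing as a count outside the percentage base, and say so in Section 4.1 so that its two sentences agree.
4. Correct the male-only footnote on the QTcF row. Either base the row on all measured subjects, or split it by sex with matching numerators and denominators. Attach or delete the female footnote, which no row currently cites.

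Leave the TEAE table notes as they are. The cost is edits to the notes, one sentence in Section 4.1 and an n row per visit. No new data or analyses are needed.
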